Professor of Biostatistics
University of Texas School of Public Health at Houston

2. Study Sites

10 Level I Adult Trauma Centers

- 4-5 with blood products on helicopters
- 4-5 with only crystalloid on helicopters

3. Overview:

The Prehospital Resuscitation On Helicopter Study (PROHS) is a pragmatic, multicenter, prospective observational study of air ambulance-based prehospital resuscitation regimens currently utilized at the participating sites. Patients will be enrolled at participating sites that currently have blood products available on air ambulances and other sites that do not. This study will not change the current prehospital standard of care for resuscitation. The primary outcome will be in-hospital mortality and the primary unit of analysis will be the patient. Other outcomes of interest will include time to hemostasis, hospital length-of-stay, number of ventilator-free and ICU-free days, incidence of major surgical procedures, complications (transfusion-related acute lung injury [TRALI], acute kidney injury [AKI], multiple organ failure [MOF], acute respiratory distress syndrome [ARDS], sepsis, intra-abdominal complications, thromboembolic complications, compartment syndromes), lifesaving interventions, the amount and type of blood products and concentrates transfused (including prehospital), wastage of prehospital blood products and concentrates, use of external and internal hemostatic devices, and functional status at discharge/discharge destination.

4. Hypothesis and Specific Aims:

The objective of this study is to compare the effectiveness of two different existing prehospital resuscitation approaches in severely injured trauma patients transported by air ambulance in a pragmatic, multicenter, prospective observational study. Hypothesis: Patients with severe traumatic injuries who are evacuated to a Level I trauma center on air ambulances and who receive plasma and/or red blood cells (RBCs) (Group 1) will have lower in-hospital mortality compared to patients evacuated on an air ambulance and who don't receive any prehospital blood products (Group 2).

Aim 1.1 Compare routinely collected prehospital vital signs and demographics, prior to in-transit resuscitation to assess whether groups were similar at baseline.

Aim 1.2 Compare in-hospital mortality and time to death between groups, adjusting for potential confounders including center.

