placed on LF air ambulances, with 1.9% wastage. Prehospital transfusion was associated with improved acid base status on hospital admission, decreased use of blood products over 24 hours, a reduction in the risk of death in the sickest patients over the first 6 hours after admission and negligible blood product wastage. In this small single center pilot study, there were no significant differences in 24-hour (odds ratio 0.57, $p=0.117$) or 30-day in hospital mortality (odds ratio 0.71, $p=0.441$) between LF and OA. In conclusion, prehospital plasma and RBC transfusion were associated with improved early outcomes, negligible blood product wastage, but not an overall survival advantage. One limitation to this single-site study was the inability to completely adjust for injury severity because the patients who received prehospital blood were consistently the most seriously injured. This indication bias can be minimized in a multisite study where some sites do not have prehospital blood available and therefore similar severely injured patients who did not receive blood will be available to compare to patients receiving prehospital blood. Similar to the data published from the ongoing war, improved early outcomes are associated with placing blood products prehospital, allowing earlier infusion of lifesaving products to critically injured patients.^{23,25}

6. Research Design:

This is a pragmatic, observational, multi-center clinical observational study that will observe and evaluate the effectiveness of two different prehospital (air ambulance only) resuscitation regimens for severely injured trauma patients. The two groups are 1) plasma and/or RBCs, and 2) no plasma or RBCs.

6.1. Study Population:

The target population for this study is trauma patients who are transported to one of the participating Level I trauma centers via air ambulance, directly from the scene, and meet the eligibility criteria listed below.

6.2. Setting:

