Site Training	✓			
IRB approval	✓			
Enrollment		✓	✓	
On-going Data Analysis		✓	✓	✓
Study Close-out				✓

9.3. Sample Size:

The primary hypothesis of this clinical study is that patients with severe traumatic injuries who are evacuated to a Level I trauma center on air ambulances and who receive plasma and/or red blood cells (RBCs) (Group 1) will

have lower in-hospital mortality compared to patients evacuated on an air ambulance and who don't receive any prehospital blood products (Group 2).

Preliminary data indicates that we can expect Group 1 to experience an in-hospital mortality rate of 34%.³² The mortality of the untreated group is unknown because of the difficulty in validly estimating mortality among patients who are at highest risk of death due to hemorrhage in the prehospital setting. The mortality rate provided is from a study performed at Memorial Hermann Hospital (MHH) in Houston, where blood products have been available on helicopters for two years. In this study, helicopter-transported patients who did not receive blood products were not as severely injured as helicopter-transported patients who did and therefore the estimate of mortality for this group is not accurate for patients at highest risk of bleeding to death. There has been no study to date that prospectively identifies patients at high risk of death due to hemorrhage during prehospital transport. One of the goals of this observational study is to accurately estimate mortality in the untreated group for use in designing a future clinical trial of prehospital blood transfusion. Finally, because this is an observational study of all available patients within 12-18 months, we will perform posterior power calculations to assess whether our preliminary sample size and mortality estimates were reasonable.

Based upon calculations found in Section 9.1, Availability of the Study Population, we expect a total sample size of 1000 patients. This number includes patients who receive blood as well as highest-risk patients who do not receive blood. Assuming that the patients who receive blood and those who do not receive blood will be distributed equally (500 in each group), we will have 90.1% power to detect a clinically meaningful difference of 10%, given a two-sided test of difference in proportions with an α -level of 0.05. This assumes no loss to follow up.³⁴

10. Analysis Plan:

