We will analyze in-hospital mortality as a fixed point in time using a Mantel-Haenszel statistic stratified by site. We will also test homogeneity of the risk ratios across sites using the Breslow-Day test. We will compute 95% confidence intervals on mortality by group. To provide further insight we will compute Kaplan-Meier survival curves.³⁶ To compare survival between groups, we will use Cox proportional hazards regression,^{37, 38} adjusting for confounders. We will further explore heterogeneity by site and consider adjusting for site as a covariate or a random effect in any regression model as appropriate. Additional site-level covariates will also be considered if they are found to contribute to a difference in effect by site. Before interpreting the Cox analyses, we will test for proportional hazards. Further details can be found in the statistical analysis plan.

Covariate Adjustment

We will compare hazard rates for mortality between groups adjusting for confounders. If heterogeneity by site is evident, we will adjust for site as a random effect or adjust for other site-level variables in multi-level models if necessary. All patient characteristics and interventions present and ascertained during prehospital transport are eligible to be included as a confounder. We will screen the following variables as potential confounders: age, gender, race/ethnicity, trauma center, severity and type of injury, prehospital vital signs and laboratory results, platelets and other pre-hospital blood product components, procoagulants and prehospital interventions (e.g., external and internal hemostatic devices, etc.). In a previous observational multicenter trauma transfusion study,²⁶ identified confounders included: age, total blood product units transfused, injury severity score, site of bleeding, and trauma center.

In addition to the primary analysis proposed we will explore the use of propensity score matching^{39,40} to adjust for confounding variables that might affect the mortality of those patients receiving prehospital blood products vs those who did not.

10.1. *Exploratory cost assessment analysis:*

We will perform a “piggy-back” economic study on the study. This will include the collection of ICD-9 code data that will allow estimation of severity-specific cost of an admission. We will use decision analysis modeling to estimate lifetime economic cost and consequences expected for the outcomes subgroups within the study.

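### The confounder rule has no cut-off at the first prehospital unit, so the adjusted mortality comparison may condition on consequences, or on parts, of the exposure

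*Protocol*

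**What the plan says.** Section 10 of the Protocol (Covariate Adjustment) sets the rule for the adjusted comparison of death hazards: "All patient characteristics and interventions present and ascertained during prehospital transport are eligible to be included as a confounder". The variables to be screened include prehospital vital signs and laboratory results, with no time of measurement given, and "platelets and other pre-hospital blood product components, procoagulants and prehospital interventions". The section then cites a previous multicentre observational transfusion study whose confounders were "age, total blood product units transfused, injury severity score, site of bleeding, and trauma center".

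The groups are defined in two ways. The hypothesis (Sections 4 and 9.3) is that Group 1 will "have lower in-hospital mortality compared to patients evacuated on an air ambulance and who don't receive any prehospital blood products (Group 2"). Section 6 says: "The two groups are 1) plasma and/or RBCs, and 2) no plasma or RBCs".

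A time limit appears only in Aim 1.1 (Section 4), for the check of baseline similarity: "Compare routinely collected prehospital vital signs and demographics, prior to in-transit resuscitation". Section 8.2 counts the amount and type of products, prehospital ones included, among the outcomes.

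**The concern.** A confounder has to precede the exposure. Here the exposure happens inside the window from which confounders may be drawn. A blood pressure taken after the first unit, or a device applied after it, may be a result of the transfusion. Conditioning on it takes that pathway out of the group effect.

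Blood components raise a second problem. If Group 2 receives no prehospital product at all, every product covariate is zero there and varies only in Group 1. The group coefficient is then an extrapolation to zero units among transfused patients, which is not the contrast of receiving blood versus not receiving it.

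The adjusted result matters in this study. Aim 1.2 calls for a mortality comparison adjusted for confounders, and Sections 5.1 and 9.3 say that transfused patients in the pilot were the more severely injured. The Mantel-Haenszel test stratifies by site only, so the Cox model is the main analysis that deals with patient-level confounding. Section 5 also wants realistic effect sizes for later trials.

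**Working it through.** **1. The plan's own figure.** Inputs from Section 9.3: 500 per group, 34% mortality in Group 1, a 10-point difference (44% in Group 2), two-sided α of 0.05.

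- Pooled proportion: (0.34 + 0.44)/2 = 0.39.
- Null SE: √(2 × 0.39 × 0.61/500) = 0.0308.
- Alternative SE: √(0.34 × 0.66/500 + 0.44 × 0.56/500) = 0.0307.
- Power: Φ[(0.10 − 1.96 × 0.0308)/0.0307] = 90.1%, as stated.

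This is a calculation for unadjusted proportions. The confounder rule does not enter it.

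**2. The texts side by side.**

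| Item | Adjustment rule (Section 10) | Elsewhere in the Protocol |
|---|---|---|
| Vital signs, laboratory results | Any taken during transport | Aim 1.1: vital signs only from before in-transit resuscitation |
| Prehospital blood components | Screened as confounders | Sections 4 and 9.3: none in Group 2; Section 8.2: outcomes |
| Hemostatic devices | Screened as confounders | Section 8.2: outcomes |

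No section carries the Aim 1.1 limit into Section 10. The pilot in Section 5.1 links prehospital transfusion to better acid-base status on admission and to "decreased use of blood products over 24 hours". These are associations only, but they make it plausible that physiology and product use change after the exposure.

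**3. Illustration: a post-start vital sign.** The documents do not give the share of effect that runs through such a variable, so the share is assumed. The model is logistic: severity S is standard normal and fully measured, treatment is more likely with higher S, and the total treatment effect on the log-odds is −0.5 before marginalising over the vital sign. If a share m runs through the vital sign, adjusting for it leaves exp[−0.5 × (1 − m)].

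| Share m | Adjusted for severity only (simulated) | Vital sign added (formula) | Vital sign added (simulated) |
|---|---|---|---|
| 25% | 0.62 | exp(−0.375) = 0.69 | 0.69 |
| 50% | 0.61 | exp(−0.25) = 0.78 | 0.78 |
| 75% | 0.61 | exp(−0.125) = 0.88 | 0.88 |

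**4. Illustration: number of prehospital units.** With n = 1,000, units are zero throughout Group 2, at least one in Group 1, and have no effect of their own. Their correlation with group is about 0.80. Adding them raises the SE of the group log-odds ratio from 0.149 to 0.236. The variance ratio is (0.236/0.149)² ≈ 2.5.

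**5. Does the direction hold if severity is poorly measured?** A separate assumed logistic model has confounding by indication, half the effect mediated, and a true odds ratio of about 0.64.

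- Severity reliability 0.9: adding post-start blood pressure moves the odds ratio from 0.71 to 0.87, away from the truth.
- Severity reliability 0.3: it moves from 1.14 to 1.06, slightly nearer the truth, because the blood pressure also stands in for unmeasured severity.

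**The case against.** The best defence is that the rule only makes variables eligible for screening. Section 10 refers to a statistical analysis plan for details, and that plan is not at hand; the timing and final choice of covariates could be settled there. This stands as far as it goes: the Protocol does not say that any post-transfusion variable will be in the model. But it states an affirmative rule with the wrong window, and a narrower plan would contradict it. A variable linked to both group and death is also likely to pass a screen based on association.

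Four stronger readings are tempting, and the documents do not support them.

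- **Adjustment will pull the estimate toward no effect.** Step 5 shows that this depends on how well severity is measured. Sections 5.1 and 6.5 admit incomplete severity adjustment and minimal prehospital diagnostic tools.
- **Total units transfused is on this study's list.** It is cited only as a finding of another study, and in-hospital units fall outside a rule limited to transport.
- **Product covariates are always zero in Group 2.** This follows from Sections 4 and 9.3. Under the definition in Section 6, a Group 2 patient could have received platelets, which could then be argued to be a co-intervention.
- **The adjusted Cox model is the only guard against confounding.** Propensity matching, the trauma-quality-programme risk adjustment and the site-level analysis of the at-risk population (Sections 10 to 10.3) are also planned, though as exploratory work.

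**Conclusion.** The point holds as a defect in the stated rule. As written, the rule admits variables that transfusion may have affected, together with products that are part of the exposure or tied to it. Following it could bias the main patient-level adjusted comparison or make it less precise, and could carry into the propensity score.

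Neither the size nor the net direction can be fixed from the documents, because both the mediated share and the quality of severity measurement are unknown. The shifts from about 0.61 to 0.69, 0.78 or 0.88 assume shares of 25%, 50% and 75%, fully measured severity, and a logistic rather than a Cox model. The 2.5-fold variance assumes units with no effect of their own. The Mantel-Haenszel test and the 90.1% power are untouched.

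**What to change.** Amend the Covariate Adjustment text in Section 10 as follows.

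1. Limit confounders to characteristics fixed at injury, even if scored later, and to vital signs, laboratory values and interventions recorded before the first prehospital unit. Valid pre-transfusion transport variables stay in.
2. Define a comparable time point in both groups. Either use the first recorded set in both, or use pre-transfusion values in Group 1 with Group 2 values matched on time since crew contact. Pre-transfusion values in Group 1 set against the first recorded set in Group 2 would measure the groups at different points of transport and bring in a new bias.
3. Remove prehospital blood components from the confounder list and report them as description of the exposure or as outcomes. Reconcile the two definitions of Group 2 (Sections 4 and 9.3 against Section 6).
4. State that total units transfused will not be used as a confounder here.
5. Apply the same variable list to the propensity score.

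The cost is mainly wording. Section 7.2 already takes prehospital data for the highest-risk subset from run sheets and crews; it should be confirmed that clock times for vital signs, interventions and the first unit are captured. The price is that later in-flight values go unused, and early values may be missing more often.

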Level I adult trauma centers will participate in this study. Approximately eight to ten centers will be selected based on their current prehospital resuscitation procedures aboard their air ambulances and other factors including annual number of patients transported. Currently, some Level 1 trauma centers have blood products available on their air ambulances, while others do not. It is not the intent of this study to change current prehospital practice at the participating centers, but to leverage the differences that already exist. For this reason, some sites will be chosen that currently have blood products available on air ambulances and some will be chosen that do not. Sites will be chosen so that the number of patients transported by air ambulance per year will be similar in the sites that have blood products and the sites that do not. However, the primary unit of analysis is the patient, not the site. Therefore, the primary analysis will examine mortality in patients who received blood prehospital compared to those who did not, adjusted for center. Air ambulances must be staffed at a minimum with EMT-Ps and nurses with the capability to transfuse blood products, and sites will be objectively balanced based on their patient volumes, outcomes, geographical distribution and the ability to submit standardized data to TQIP. The participating sites must agree to not change their prehospital resuscitation regimens during the enrollment phase of the study. No other trauma care variable will be controlled. Furthermore, to minimize the confounding variables of transport time and level of available prehospital care and to contribute relevant data to the military system, this study will be performed on air ambulance transports only.

6.3. Inclusion Criteria (At-risk population):

Patients meeting the following inclusion criteria will be enrolled in this study.

- 1) Patients with traumatic injuries received directly from the scene via air ambulance service (did not receive a lifesaving intervention at an outside hospital or healthcare facility)
- 2) Estimated age of 15 or older or greater than/equal to a weight of 50 kg, if age unknown

6.3.1. Subset Inclusion Criteria (Highest risk population):

Patients meeting the following inclusion criteria will be followed for direct observation data collection after hospital admission.

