patients, allowing robust risk adjustment between participating trauma centers. As much as possible the TQIP registry data at each site will be leveraged, minimizing the double collection of standard trauma data. We have confirmed that TQIP (personal communication with [name]) will provide state-of-the-art risk adjustment among participating centers.

8. Study Outcome Measures:

8.1. Primary Outcome:

The primary outcome will be in-hospital mortality. In an unpublished single site retrospective study of prehospital blood transfusions, 30-day in-hospital mortality was 34% among patients who received prehospital blood products.

8.2. Additional outcomes of interest:

Additional outcomes of interest include time to hemostasis, hospital length-of-stay, number of ventilator-free and ICU-free days, incidence of major surgical procedures, complications (TRALI, AKI, MOF, ARDS, sepsis, intra-abdominal complications, thromboembolic complications, compartment syndromes), lifesaving interventions, the amount and type of blood products and concentrates transfused (including prehospital), wastage of prehospital blood products and concentrates, use of external and internal hemostatic devices, and functional status at discharge/discharge destination.

9. Projected Enrollment:

9.1. Availability of Study Population:

We have received preliminary estimates of the source population from potential sites. Using an average of 473 patients/year transported by air ambulance at each potential site, we expect over 7000 at risk patients at ten participating sites during an 18-month enrollment period. We will collect registry data on all these patients. Additionally, we expect 15% percent of this population to potentially require blood products prehospital,^{25, 32} resulting in approximately 1000 patients meeting highest risk inclusion criteria (the population of focus in this study). Based on our experience with three consecutive multicenter transfusion studies over the last eight years (totaling 70,000 screened and > 2500 transfused and enrolled patients) the mortality among the sickest patients (those who receive prehospital blood products), mortality will reach 34%.

9.2. Timeline:

We estimate PROHS to run over a 3 year time period which includes a 6 month start-up period followed by an 18 month enrollment period followed by a 1 year data analysis period.

Activities	Period 1 6/14 – 12/14	Period 2 1/15-12/15	Period 3 1/16-12/16	Period 4 1/17-6/17
Planning	✓			

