10.2. *Trauma Quality Improvement Program (TQIP):*

We will facilitate data exchange with TQIP, who will provide state-of-the-art risk adjustment among participating centers as an exploratory analysis.

10.3. *Exploratory analysis of overall at risk population:*

Exploratory data analyses making use of the larger data set for the entire at-risk study population will examine overall between-group differences in mortality adjusted for injury and bleeding severity covariates (e.g., by direct standardization and multivariable Poisson regression). In this analysis, group A is defined as sites with pre-hospital blood products available and group B is defined as sites without pre-hospital blood products available.

11. Data Management:

All subjects will be identified by a study number only. All hard copies of source documentation will be kept in a secured, locked cabinet in a secure area. All electronic copies of source documentation will be maintained on a secure password computer. The study specific electronic data will be entered and maintained on a password protected web-based program designed for this study. All study documents will be maintained at the sites for at least two years after study completion unless superseded by participating site’s requirements.

The data entered for the PROHS study will be maintained at the HDCC in a relational database cluster. The cluster is composed of multiple servers, which provide redundant access to the data in the event of a hardware failure to one of the servers. This cluster is maintained behind a firewall, which is not accessible from the internet without a secure network connection. The data will be backed up nightly and copies of the data will be routinely stored off site in a secure vault. In addition to the data servers, the production web server will also be backed up routinely. The separate development web server will serve as a backup to the production server.

11.1. *Error Checking:*

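### The pooled whole-population contrast in section 10.3 dilutes a blood effect to about 1.5 points but leaves site differences undiluted; adding the same contrast by risk stratum would make it easier to interpret

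*Protocol*

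**What the plan says.** Section 10.3 of the protocol, headed exploratory, uses the entire at-risk population and "will examine overall between-group differences in mortality adjusted for injury and bleeding severity covariates", for example by direct standardization or Poisson regression. Exposure is a property of the site: "group A is defined as sites with pre-hospital blood products available and group B is defined as sites without pre-hospital blood products available". Section 10.3 names no site-level covariate, site effect or split by risk.

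The relevant figures are elsewhere in the protocol:
- Section 2 lists "4-5 with blood products on helicopters" and the same number without.
- Section 9.1 assumes a mean of 473 helicopter patients per site and year, and from this a total above 7000 for ten sites over 18 months. On need it says: "we expect 15% percent of this population to potentially require blood products prehospital".
- Section 9.3 takes a 10-point mortality difference as clinically meaningful.
- Section 6.2 says "No other trauma care variable will be controlled". It also says that sites will be balanced on volume, outcomes and geography.
- Section 10 allows site, as a covariate or random effect, or site-level covariates in regression models where heterogeneity calls for them.
- Section 10.2 adds a separate exploratory risk adjustment among centers.

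**The concern.** Section 5.1 gives the reason for a multisite design: in the single-center study the transfused patients were the most severely injured, and sites without blood supply comparable untransfused patients. Section 10.3 is the analysis that defines groups by availability rather than receipt, so the crew's choice of whom to transfuse does not define its groups.

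Taking that contrast over everyone weakens it in two ways. Most patients are not expected to need blood, so any effect is diluted. Any general difference in care between the two sets of sites applies to all patients and is not diluted. Adjusting for a patient's injury and bleeding severity does not capture hospital quality. A positive result could then reflect site differences, and a null result could reflect dilution. The lower-risk patients could help tell these apart, but the plan only pools them with the rest.

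**Working it through.** **1. The plan's own figures.** 473 × 10 sites × 1.5 years = 7095 patients, and 15% of that is 1064; both agree with section 9.1. With "number of patients transported by air ambulance per year will be similar in the sites that have blood products and the sites that do not", each side has about 7095 / 2 = 3548. The 90.1% power in section 9.3 reproduces for 34% versus 44% with 500 per group (pooled normal approximation, two-sided 0.05). No power is stated for section 10.3.

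**2. Dilution.** Overall difference = share treated × effect in the treated.
- 15% (section 9.1): 0.15 × 10 = 1.5 points.
- 14.1% (500 / 3548): 1.4 points.
- 19% (section 5.1, in a cohort already restricted to transfused patients): 1.9 points.
- Half of the 15% treated: 0.75 points.

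**3. What a site gap looks like.** With no blood effect, a uniform gap g reads as g / 0.15 per treated patient. Gaps of 0.5, 1.0, 1.5 and 2.0 points read as blood effects of 3.3, 6.7, 10 and 13.3 points.

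**4. Noise between sites.** Assumptions, not in the protocol: overall mortality 10%, and between-site SD τ after adjustment. With 5 sites per side, variance of the difference = 2τ²/5 + binomial variance.
- No site noise: SE = √[(0.10 × 0.90 + 0.085 × 0.915) / 3548] = 0.0069, and power for 1.5 points is 59%. It is 88% at 5% mortality and 44% at 15%.
- τ = 1 or 2 points: power falls to 36% or 18%.
- No blood effect and a patient-level test with no site term: rejection at nominal 5% is 7%, 14%, 34% and 49% for τ = 0.5, 1, 2 and 3 points.

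**5. Pooled contrast against the stratum interaction.** Simulation with assumed inputs: 10 sites × 710 patients, site SD 0.2 on the log-odds scale, mortality 42% in the 15% at highest risk and 4% in the rest, and a site-level t-test, so clustering is already handled.

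| Scenario | Overall contrast rejects | Availability-by-stratum interaction rejects |
|---|---|---|
| No blood effect, uniform site gap, OR 0.85 / 0.75 | 15% / 36% | 5% / 5% |
| No blood effect, site gap in highest-risk stratum only, OR 0.85 / 0.75 | 7% / 14% | 12% / 28% |
| 10-point benefit, all highest-risk treated | 24% | 55% |
| 10-point benefit, half treated | 10% | 18% |

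In the low-risk stratum alone, the site contrast detects the uniform gap about 13% / 27% of the time. It rejects 4-5% of the time when the gap is confined to the highest-risk stratum. If the criteria are loose, with 34-59% of flown patients qualifying, power is 8-16% overall and about 15% for the interaction.

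**The case against.** Section 10.3 is labelled exploratory and promises only to examine overall differences. An availability contrast over all patients is a legitimate descriptive quantity, and dilution is not bias. The hypothesis and primary analysis concern receipt of blood. All of this stands, and it limits the weight of the point.

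The protocol also has mitigations: balanced site selection, optional site terms and the separate risk adjustment in section 10.2. They are real but partial. Exposure is constant within a site, so fixed site effects are collinear with the grouping. A random site effect widens the interval but leaves a systematic gap in place. Balancing on outcomes with 4-5 sites per side cannot ensure equal quality, and outcomes at blood sites may already contain any blood effect.

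The strongest objection concerns the remedy. A reader might infer that the interaction between availability and risk stratum should replace the overall contrast as the reported effect. The documents do not support that. The interaction removes site confounding only if site differences act alike in both strata. Sections 5 and 5.1 describe hospital practices aimed at bleeding patients, such as plasma in the emergency department and damage control resuscitation, which could break this assumption. The second row of the table shows the interaction then doing worse than the pooled contrast while the low-risk check looks clean.

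The power gain is also uncertain. Section 6.5 reports that 54% of untransfused patients met at least one of four criteria, so the highest-risk stratum may be far larger than 15%. Some criteria are themselves crew actions.

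**Conclusion.** The point holds as a limitation of an exploratory analysis with an inexpensive improvement. On the protocol's own 15% and 10 points, a blood effect shrinks to about 1.5 points in the pooled contrast, while a general site gap keeps its full size.

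Two stronger readings should be avoided. A reader might take 15% as a ceiling on who can benefit; the protocol gives it as an expectation, though 19% would still yield only 1.9 points. A reader might also conclude that section 10.3 can say nothing about blood. What follows is narrower: taken alone, the pooled contrast separates a blood effect poorly from site differences.

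The dilution figures rest on protocol numbers. The overall mortalities and τ in step 4, and the 42% and 4% mortalities, site SD of 0.2 and odds ratios in step 5, are assumptions. The 15% / 36% rejection rates follow directly from an assumed gap favoring blood sites.

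**What to change.** Keep the overall contrast in section 10.3 as description and add, with inference at the level of the site:
- (a) blood versus no-blood sites in patients who met at least one of the six prehospital criteria in section 6.3.1 or were transfused before hospital arrival;
- (b) the same contrast in patients who met none and were not transfused, as a check on general site differences;
- as a sensitivity analysis only, the availability-by-stratum interaction, with the log-odds scale named in advance.

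Counting transfusion as a criterion can move patients only at blood sites, so repeat the strata without it. If (b) is clearly not zero, say that site differences confound the availability comparison.

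State the limits in the plan. The interaction needs site differences to act alike in both strata. Check (b) has low power, so a null result there does not show that confounding is absent. Some criteria depend on crew practice. The power gain largely disappears if the criteria are loose.

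The cost is wording in section 10.3 or the SAP and a little more analysis. No patients are added: section 7.1 has eligibility ascertained on arrival, and section 7.2 lists prehospital vital signs and lifesaving interventions among the registry data.
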